4.1 Study Design Overview

4.1.1 Primary study design

This study employs a two-arm, parallel-group, assessor-blinded randomised controlled trial (RCT), with 1:1 allocation to the intervention and control groups. Outcome assessors are blinded to group assignment to minimise measurement bias. The protocol and reporting adhere to the CONSORT 2010 Statement, including transparent documentation of randomisation sequence generation, allocation concealment, blinding, and participant flow.

4.1.2 Nested sub-study designs

Six sub-studies are nested within the primary RCT framework. Sub-study 1: predictive model development (TRIPOD guidelines). Sub-study 2: observational dose–response analysis (STROBE statement). Sub-study 3: causal mediation analysis using a counterfactual framework. Sub-study 4: interaction-effect analysis via mixed-effects modelling with interaction terms. Sub-study 5: longitudinal trajectory modelling using group-based trajectory modelling (GBTM) or latent class growth modelling (LCGM). Sub-study 6: trial-based economic evaluation with ICER calculation (CHEERS checklist).

4.1.3 Study setting

The study will be conducted at smart community elderly care service centres in Ke'erqin District, Tongliao City, Inner Mongolia Autonomous Region, China. These centres serve typical urban residential communities with large retired populations and established smart elderly care pilot infrastructure. Community sub-district offices will assist with participant recruitment, and licensed rehabilitation therapists will serve as consultants. Tongliao City Hospital orthopaedics department will provide DXA equipment support and medical advisory services.

4.2 Participants

4.2.1 Inclusion criteria

Eligible participants must: (1) be aged ≥ 60 years (either sex); (2) have a DXA-confirmed diagnosis of primary OP (lumbar spine or hip T-score ≤ -2.5 , or ≤ -2.0 with a fragility fracture history); (3) reside in the designated community with no relocation plans within one year; (4) demonstrate adequate cognitive function (MMSE ≥ 24 , adjusted for education level); (5) be

independently ambulatory (assistive devices permitted; severe motor impairments excluded); (6) provide written informed consent; and (7) have confirmed primary OP (secondary OP excluded).

4.2.2 Exclusion criteria

Exclusion criteria include: (1) recent major medical events (fracture, hip/spine surgery within 3 months, or uncontrolled cardiovascular disease within 6 months); (2) current participation in comparable exercise programmes or clinical trials; (3) terminal illness with estimated survival <1 year; (4) inability to complete 12-month follow-up (planned relocation); (5) severe sensory or communication impairments precluding training participation; (6) other conditions deemed unsuitable by investigators (e.g., severe alcohol dependence); and (7) lack of family/caregiver support.

4.2.3 Recruitment process

Recruitment proceeds through multiple community channels. The smart elderly care centre databases collectively cover 8,736 residents aged 60+, of whom 2,619 carry an OP diagnosis. Community sub-district offices co-host health seminars and post recruitment notices; community clinic physicians identify potentially eligible patients. Interested individuals undergo telephone pre-screening. Those preliminarily eligible attend an in-person enrolment assessment at the community centre, where they provide informed consent, undergo inclusion/exclusion verification, and complete baseline evaluations (DXA, functional tests, questionnaires). Eligible participants are then randomised via computer-generated random sequence. The entire process is documented in a CONSORT flow diagram.

4.3 Intervention Protocol and Control Measures

4.3.1 Intervention group (smart community resistance training)

Table 4.3.1 (1), Resistance training program

Program Framework	Implementation Methods	Specific content	
Pre-implementation assessment	The researchers, orthopedic physicians, and nurses jointly evaluated	1. Detailed medical history and physical examination to exclude contraindications to exercise (such as severe cardiovascular disease, history of cerebral infarction, etc.) 2. Muscle function, exercise ability, exercise level, etc. 3. Whether there are diseases that restrict exercise, such as knee osteoarthritis, bone deformity, etc., whether there are mental disorders, intellectual disabilities, etc.	
Resistance Training Program		Exercise intensity	Moderate intensity (12-13 points on the PRE scale)

			
- Starting intensity: 50-60% 1RM (RPE 3-4)
 
- After advancement: 70-80% 1RM (RPE 5-6)
 
- Breathing principle: exhale with force, inhale with relaxation

		Exercise frequency	
3 times/week, 1-2 sets of each exercise, 10-15 repetitions per set;
 
1-4 weeks 1 set of each exercise (10-15 repetitions/set)
 
5-12 weeks 2 sets of each exercise (10-15 repetitions/set)
 
Based on the training manual

		Exercise time	
5 minutes of warm-up, 40 to 60 minutes of resistance training (including interval rest time, 2 to 3 minutes rest between each set), and 5 minutes of stretching and relaxation.

		Sports Tools	
4 types of elastic bands.
 
Yellow is 10 pounds (about 4.5 kg)
 
Pink is 15 pounds (about 6.75 kg)
 
Blue is 20 pounds (about 9.07 kg)
 
Purple is 30 pounds (about 13.6 kg)
 
According to the patient's repetition of 10 to 15 times combined with the PRE dosage to reach a moderate intensity, the elastic band with corresponding load is given.

		Specific actions	
1. Warm-up exercises: including neck stretching, chest expansion exercises, hip rotation exercises, knee twisting exercises, and marching in place, etc.
 
2. Resistance exercises: including waist and back exercises, lower limb exercises, and upper limb exercises. See Table 4.3.1 (2) for specific resistance exercise movements
 
3. Relaxation: stretching, massaging, patting, shaking, and relaxing the limbs with breathing.

		Precautions	
1. Do not hold your breath during training to prevent cardiovascular disease
 
2. When exercising, pay attention to inhaling when exerting force and exhaling when relaxing
 
3. After exercise, use the smart health bracelet to remind the elderly to fill in the exercise diary.

		
4. Before exercise, self-assess whether there are any discomfort symptoms, blood pressure and blood sugar control, and stop exercising if you feel uncomfortable
 
5. If the patient experiences dizziness, chest tightness, difficulty breathing and other discomfort symptoms during exercise, stop exercising immediately and contact the researcher immediately
 
6. Gradually increase the intensity of exercise to ensure patient tolerance.

Health Education Program	Expert Lectures	
1. Definition, classification and harm of the disease, etc., to make patients aware of the susceptibility of the disease
 
2. The effect of exercise on osteoporosis and the harm of inactivity, etc., to make patients aware of the benefits of exercise and the severity of inactivity
 
3. Analyze the patient's current movement disorders, gradually eliminate the obstacles they may encounter, and correct incorrect cognition

	1 offline group class per month	
1. Patients share their current feelings about exercise and the obstacles they encounter
 
2. Patients with strong exercise execution ability share their experiences
 
3. Review the effects of exercise
 
4. Provide supplementary health education

	Once a week, offline action guidance, error correction and adjustment	
1. Ask patients about their individual differences in the implementation of the plan
 
2. Encourage patients to keep exercising
 
3. Understand and guide patients on how to master exercise methods, and timely micro-control the amount of exercise
 
4. Export the patient's health data and exercise status analysis for this week through the smart bracelet data platform and use the data to make patients more confident to continue to persist.
 
5. Ask patients about their exercise status in the past week and encourage them to express their feelings about exercise.
 
6. Emphasize precautions during exercise to ensure patient safety

The intervention follows the FITT-VP exercise prescription principles. Frequency: 3 sessions/week. Time: 5-minute warm-up, 30–50 minutes of RT (including 2–3 minutes inter-set rest), 5-minute cool-down stretching. Type: moderate-intensity whole-body resistance exercises targeting weight-bearing muscle groups. Intensity: initial 50–60% 1RM (RPE 3–4),

progressing to 70–80% 1RM (RPE 5–6). Volume: weeks 1–4, one set per exercise (10–15 repetitions); weeks 5–12, two sets per exercise. Equipment: colour-coded elastic resistance bands (yellow 10 lb/4.5 kg; pink 15 lb/6.75 kg; blue 20 lb/9.07 kg; purple 30 lb/13.6 kg), assigned based on baseline functional assessment.

Table 4.3.1 (2), Specific resistance exercise movements 具体抗阻运动动作

Action name (muscle group exercised)		Key Points
Lower back exercise 腰背部运动		
1	Back stretch (Sacrospinal muscles)	Lie prone, place a pillow under your abdomen, put your arms at your sides, use your back strength to lift your upper body, hold for 3 to 5 seconds, then slowly lower it. Rest for 2 to 3 minutes between sets
Lower limb exercise 下肢运动		
2	Band prone position Knee flexion (hamstrings, etc.)	Lie prone, fix the ankle joint with an elastic band, fix the left leg, bend the right knee as much as possible, hold for 3 to 5 seconds, then slowly lower it. Alternate between left and right for 1 to 2 sets. Rest for 2 to 3 minutes between sets
3	Elastic band supine straight leg raise (quadriceps, etc.)	Supine position, fix the ankle joint with an elastic band, fix the left leg, dorsiflex the ankle joint of the right leg, straighten and lift until you can't go any further, hold for 3 to 5 seconds and then slowly lower, fix the pelvis and lumbar spine with both hands. Alternate between left and right for 1 to 2 sets each. Rest for 2 to 3 minutes between sets
4	Elastic band sitting thigh abduction (gluteus Medius, etc.)	Sit with your hands behind your back, keep your back straight, fix your ankles with an elastic band, straighten your legs, keep your left leg still, and stretch your right leg as far out as possible until you can't go any further, hold for 3 to 5 seconds, then slowly retract. Alternate between left and right for 1 to 2 sets. Rest for 2 to 3 minutes between sets
5	Elastic band seated knee extension (quadriceps, etc.)	Sit on a chair, tighten your abdomen, straighten your back, fix your ankle with an elastic band, keep your left leg still, and stretch your right leg forward. Hold for 3-5 seconds and then slowly lower it. Alternate between left and right for 1-2 sets. Rest for 2-3 minutes between sets.
6	Elastic band ankle plantar flexion (calf muscles)	Sit, fix one end of the elastic band to the forefoot of both feet, tighten the other end with both hands, and plantar flex until you can no longer continue, hold for 3-5 seconds and then slowly put it down. Repeat. Rest 2-3 minutes between sets
7	Elastic band ankle dorsiflexion (dorsiflexor muscles)	Sit down, support yourself with your hands behind your back, fix one end of the elastic band, and put the other end on the instep. Do the dorsiflexion until you can no longer do it. Hold for 3-5 seconds and then slowly lower it. Repeat. Rest for 2-3 minutes between sets.
Upper limb exercise 上肢运动		
8	Band arm raises (deltoids, etc.)	Sit on a chair, tighten your abdomen, straighten your back, face your palms forward, hold the elastic band tightly with both hands and pull it outward wider than your shoulders. After maintaining a certain tension, slowly stretch your hands upwards, hold for 3 to 5 seconds, and then slowly lower them. Rest 2 to 3 minutes between sets
9	Elbow flexion with elastic band (biceps, etc.)	Sit on a chair, tighten your abdomen, straighten your back, put one end of the elastic band on your thigh, hold the other end tightly with your hand, keep your upper arms close to your body and keep them still, slowly pull the elastic band up with your forearms until you can no longer continue, hold for 3-5 seconds,

		then slowly retract. Alternate between left and right for 1-2 sets. Rest for 2-3 minutes between sets
--	--	---

The training programme comprises nine exercises targeting three body regions. Lumbar-dorsal region: prone back extension (erector spinae). Lower extremity: prone knee flexion (hamstrings), supine straight-leg raise (quadriceps), seated hip abduction (gluteus medius), seated knee extension (quadriceps), ankle plantarflexion (posterior calf), and ankle dorsiflexion (anterior tibialis). Upper extremity: seated overhead press (deltoids) and seated biceps curl (biceps brachii).

Periodised progression follows dual-indicator control: volume progression (one additional set per exercise every 4 weeks, maximum 3 sets), intensity progression (resistance-band upgrade when RPE ≤ 4 with 15 standard repetitions), and density progression (inter-set rest reduced from 120 seconds to 75 seconds after week 12).

Smart components: each participant receives a Huawei Band 10 smart wristband that monitors heart rate, fall events, and blood pressure via Bluetooth synchronisation to the community health management platform. Training completion is recorded through WeChat-based manual check-in. A WeChat mini-programme delivers daily training prescriptions with illustrated guidance. The system includes automated training reminders and safety alerts (abnormal heart-rate detection triggers rest prompts and staff notification).

Personnel support: trained staff provide in-person guidance during the first week, with monthly on-site supervision thereafter. A designated team member contacts each participant weekly via WeChat to address questions and maintain adherence. Health education includes monthly group lectures and weekly one-on-one technique correction sessions.

Safety measures: pre-training medical screening (physical examination and exercise-risk assessment), individualised modifications for comorbidities (e.g., extended warm-up and blood-pressure monitoring for hypertensive patients), on-site emergency equipment (first-aid kit, AED), and a formal adverse-event reporting mechanism with monthly review and immediate reporting of serious events to the ethics committee.

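### The contraindication assessment is described only for the training arm, is not among the steps before randomisation, and names grounds that the exclusion criteria do not

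*Protocol*

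**What the plan says.** Section 4.2.3 describes an enrolment visit with consent, a check of the criteria, a DXA scan, function testing and questionnaires. It then continues: "Eligible participants are then randomised via computer-generated random sequence". No physical examination for exercise contraindications is listed.

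The medical exclusions in section 4.2.2 are "recent major medical events (fracture, hip/spine surgery within 3 months, or uncontrolled cardiovascular disease within 6 months" and, at the investigator's discretion, "other conditions deemed unsuitable by investigators (e.g., severe alcohol dependence".

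The assessment appears in section 4.3.1, under the intervention group. The first item of the pre-implementation row in Table 4.3.1 (1) reads "Detailed medical history and physical examination to exclude contraindications to exercise (such as severe cardiovascular disease, history of cerebral infarction, etc". The third item asks "Whether there are diseases that restrict exercise, such as knee osteoarthritis, bone deformity, etc., whether there are mental disorders, intellectual disabilities, etc". The safety measures for the same arm repeat the idea as "pre-training medical screening (physical examination and exercise-risk assessment". Section 4.3.2, on the control group, contains no such step.

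**The concern.** Randomisation protects the comparison only if later removals do not depend on the arm. A medical screen that is applied to one arm, on grounds wider than eligibility, opens a route to arm-dependent removal. Two of the primary outcomes (SPPB and the SF-36 summaries) and one secondary outcome (falls) plausibly relate to vascular comorbidity. If people who fail the screen leave the training arm while their counterparts stay in control, the training arm would look better without any training effect. If they stay but do not train, the estimated effect shrinks, because the trial has randomised people it did not intend to train.

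**Working it through.** The Protocol gives no figure on this point, so the check is a comparison of text.

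**1. Where the assessment sits.** It is stated twice, both times in section 4.3.1: in Table 4.3.1 (1) and in the safety measures. The second statement ties it to training, which only this arm receives. It is absent from sections 4.2.3 and 4.3.2.

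**2. Whether its grounds match eligibility.**

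| Condition | Sections 4.2.1 and 4.2.2 | Table 4.3.1 (1) |
|---|---|---|
| Cardiovascular disease | Only "uncontrolled cardiovascular disease within 6 months" | Severe disease, with no condition on control or time |
| Past cerebral infarction | Not named | Named as a contraindication |
| Knee osteoarthritis, bone deformity | Not named; severe motor impairment is excluded | To be checked (item 3); no wording of exclusion |
| Mental or intellectual conditions | Partly covered by MMSE of at least 24 | To be checked (item 3); no wording of exclusion |

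The clear mismatch is in the first two rows. Item 1 is the only one that speaks of excluding, and its list is left open-ended.

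**3. What can happen to one person.** Take someone with a past cerebral infarction who meets every named criterion. Section 4.2.3 allows randomisation. In control, nothing further applies. In the training arm, item 1 names the condition as a contraindication. The Protocol does not say whether that person is withdrawn, given adapted training, or kept in follow-up without training.

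**4. What the consequence would be.** Let p be the fraction of the training arm affected.
- If they are removed from the analysis, the raw arm mean shifts by p × (mean of those remaining − mean of those removed).
- If they are retained, do not train and gain nothing, the effect is multiplied by (1 − p).

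The Protocol supplies neither p nor the difference in means. Purely as an illustration, with p of 10% to 20% and an SPPB deficit of 2 points (both assumed), the shift is 0.10 × 2 = 0.2 to 0.20 × 2 = 0.4 points, and the multiplier is 0.9 to 0.8. The shift is in raw means. Adjustment for baseline SPPB and for the covariates in section 3.3.3, which include comorbidity burden, would reduce it. These figures show how the mechanism works and do not estimate its size in this trial.

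**The case against.** The strongest reply is that the timing is inferred. No section places the assessment after allocation, and several point towards baseline:
- The schedule in section 3.3.4 collects medical history at T0, one week before randomisation.
- Section 4.3.1 assigns the elastic bands from a baseline functional assessment.
- Section 4.6 mentions a baseline PAR-Q.
- The discretionary exclusion in section 4.2.2 could remove some of these people before randomisation.

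All of this stands as a reason for caution. It does not close the gap, because none of these steps refers to the assessment in Table 4.3.1 (1) or its grounds, and a discretionary criterion does not guarantee that both arms are treated alike. The Protocol does not give the content of the PAR-Q, so one cannot say whether it covers these conditions.

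A reader might infer three stronger points that the document does not support. The first is that the plan expels randomised participants: no withdrawal is stated, and excluding contraindications can simply mean ruling them out. The second is that knee osteoarthritis and bone deformity are additional exclusion grounds: the table only asks whether they are present, and the safety measures provide for training adapted to comorbidity. The third is that a bias in favour of training is built in: that requires removal from follow-up or analysis, which the Protocol does not state.

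It can also be said that analysis sets belong in the statistical analysis plan, and that the mixed models in section 4.5.3 accommodate incomplete data. The first is fair as far as it goes, but who is examined, when and on what grounds is enrolment procedure, which an analysis plan cannot repair. As to the second, a mixed model cannot use people who have been taken out of the analysis.

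**Conclusion.** The point holds as a defect in the enrolment procedure. The assessment is described for one arm only, is not among the listed steps before randomisation, and names two grounds missing from section 4.2.2: any past cerebral infarction, and severe cardiovascular disease without the limit to uncontrolled disease in the last 6 months. Following the text as written leaves open a loss, or a failure to train, that depends on the arm. Whether it would occur depends on two things the Protocol leaves unstated: when the assessment is done and what happens to those who fail it. Its size cannot be estimated from the document. It should be corrected before enrolment, but since neither post-allocation timing nor withdrawal is stated, it does not rank with the most serious defects. Which conditions should count as contraindications is a clinical question and is not judged here.

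**What to change.** 1. Carry out this assessment for every candidate at the enrolment visit, before randomisation, and add it to the steps in section 4.2.3.
2. Have the clinicians reconcile Table 4.3.1 (1) with section 4.2.2 into a single list, and refer to that list from both places.
3. State that anyone judged unfit to train after randomisation stays in follow-up and is analysed in the assigned arm.

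The cost is some extra examination time at an existing visit for candidates later allocated to control, plus a change of wording. Section 4.7.1 gives ethical approval as pending, so the change can be made before anyone is randomised.

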1.4 Research Objectives and Innovations

1.4.1 Overall research objective

The overarching objective is to validate the comprehensive benefits of “community-based

smart RT” for BMD, muscular function, and quality of life (QoL) among older adults with OP, and to establish a sustainable implementation pathway. Specifically: (a) quantify the effect of 8-month RT on lumbar spine BMD through an RCT, with an expected increase of $\geq 3\%$ (benchmarked against the IOF clinical significance threshold); (b) design a long-term intervention strategy with 8 months of supervised training (twice weekly) followed by 12 months of low-frequency maintenance (once monthly); and (c) develop an integrated smart elderly care system featuring real-time wearable monitoring, AI-driven exercise prescription adjustment, and community-station offline supervision, achieving “data–professional–family” three-tier coordination.

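### The protocol states three parts of the training prescription in two ways: breathing on effort, sessions per week, and sets in weeks 9–12

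*Protocol*

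**What the plan says.** **Breathing.** The Exercise intensity row of Table 4.3.1 (1) states: "Breathing principle: exhale with force, inhale with relaxation". Item 2 of the Precautions row in the same table tells participants to "pay attention to inhaling when exerting force and exhaling when relaxing". Among the weekly staff tasks listed in that table is: "Emphasize precautions during exercise to ensure patient safety".

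**Frequency.** Objective (b) in Section 1.4.1 describes "8 months of supervised training (twice weekly) followed by 12 months of low-frequency maintenance (once monthly". The exercise frequency row of Table 4.3.1 (1) gives "3 times/week, 1-2 sets of each exercise, 10-15 repetitions per set", and the prescription text below the table repeats "Frequency: 3 sessions/week".

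**Sets.** The table and the prescription text in Section 4.3.1 agree on one set in weeks 1–4, and then "weeks 5–12, two sets per exercise". The periodised progression paragraph of the same section sets a different rule: "one additional set per exercise every 4 weeks, maximum 3 sets". In Table 4.3.1 (2), five of the nine exercises (2, 3, 4, 5 and 9) still specify one to two sets.

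**Where these quantities are used.** Section 3.2.2 defines adherence through the share of planned sessions completed, and dose as cumulative training volume. Section 4.3.3 has the platform log compared weekly with the planned schedule. Section 4.4.2 lists mean adherence and mean dose as process indicators. Section 1.3.4 sets an adherence target above 70%.

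**The concern.** The breathing line matters most because it is a safety instruction to older people with osteoporosis. The Precautions row links breathing to cardiovascular safety, since the item just before the conflicting one warns against breath-holding for that reason. Section 4.6 lists exercise-induced cardiovascular events among the assessed risks. All nine exercises include a hold of 3 to 5 seconds, and intensity is meant to rise to 70–80% of 1RM. Staff and participants reading one table would find the instruction both ways, with nothing to say which is right.

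The frequency conflict matters because planned sessions are the denominator of adherence. The same attendance record gives a different percentage depending on which section supplies the plan. That carries into the reported mean adherence, and could affect the attendance-based ICER subgroups in Section 2.4.4.

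The set conflict leaves staff without a single prescribed volume for one four-week block.

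**Working it through.** The protocol gives no figure to reproduce here. The check is a side-by-side reading followed by simple arithmetic.

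**1. Breathing**

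| Place in Table 4.3.1 (1) | On effort | On relaxation |
|---|---|---|
| Exercise intensity row | exhale | inhale |
| Precautions row, item 2 | inhale | exhale |

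The two are exact opposites. The warning against breath-holding is compatible with either, so it does not settle the matter.

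**2. Frequency**

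Inputs: 2 sessions a week (1.4.1) or 3 (4.3.1). The protocol gives 8 months but no number of training weeks, so 32–35 weeks is assumed.

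Planned sessions = sessions per week × weeks:
- two a week: 2 × 32 = 64 to 2 × 35 = 70
- three a week: 3 × 32 = 96 to 3 × 35 = 105

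Adherence of someone who attends twice every week:
- against a plan of two: 2/2 = 100%
- against a plan of three: 2/3 = 66.7%

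These percentages do not depend on the assumed number of weeks, and they fall on either side of the 70% target. The 70% level itself is 0.70 × 64 = 44.8 to 0.70 × 70 = 49.0 sessions on the first plan, and 0.70 × 96 = 67.2 to 0.70 × 105 = 73.5 on the second.

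Could twice weekly mean only the supervised part of three sessions? Section 4.3.1 gives in-person guidance in week 1 and monthly on-site supervision afterwards, plus one technique-correction session a week. None of these is two supervised sessions a week for 8 months, so that reading does not reconcile the sections.

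**3. Sets in weeks 9–12**

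Inputs: 3 sessions a week, 4 weeks, and 2 sets (fixed schedule) or 3 sets (progression rule, counted from one set in weeks 1–4).

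- fixed schedule: 3 × 4 × 2 = 24 sets per exercise
- progression rule: 3 × 4 × 3 = 36 sets per exercise, and 36/24 = 1.50

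Over weeks 1–12 the totals are 3 × (4×1 + 8×2) = 60 and 3 × (4×1 + 4×2 + 4×3) = 72 sets per exercise, and 72/60 = 1.20.

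No whole-course figure is offered. The fixed schedule stops at week 12, so any total for 8 months would rest on an assumption about what follows.

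**The case against.** **Breathing.** The only breathing hazard the protocol names is breath-holding, and both versions avoid it. Nothing in the document ranks the two or shows that one causes harm. There are safeguards: weekly technique correction, unified staff training with examinations, an operations manual, and a fidelity checklist that scores technique correction. A reader might infer that a dangerous instruction is being given and that the trial cannot start until it is changed. The document does not support that. A reader might also infer that staff will repeat the conflicting line every week, but the weekly task mentions precautions only in general terms, and the same contact is meant for correcting errors. What stands is that one table states a safety instruction both ways and none of these safeguards, as described, says which is right.

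**Frequency.** The twice-weekly figure appears once, in a Chapter 1 objective. The intervention section says three in both table and text, and is plainly the operative source. The gap between 100% and 67% arises only if someone trains to one figure and is scored on the other. The 70% target sits in the background chapter and is not an outcome criterion. This lowers the weight of the conflict but does not remove it, because no planned session count is stated anywhere.

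**Sets.** The progression rule could be read as carrying volume on to the maximum after week 12. However, the paragraph attaches the week 12 start only to the shortening of rest intervals, and the step from one to two sets at week 5 already follows the four-week rule. A reader might infer that the dose variable is undefined. It is not: H2 concerns actual dose, which Section 3.3.4 takes from platform and manual logs. The conflict affects the volume prescribed, not the definition of the dose recorded.

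**Conclusion.** All three inconsistencies are in the current text and should be corrected. They are drafting errors of moderate weight.

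- **Breathing:** two opposite instructions in one table, with a harm that the document does not allow to be quantified and that existing safeguards partly reduce.
- **Frequency:** one summary line against consistent operative text. Its effect is on the adherence denominator, with 64–70 or 96–105 planned sessions on the assumed 32–35 weeks. The contrast of 100% and 67% needs no such assumption.
- **Sets:** a clarification for weeks 9–12, 24 or 36 sets per exercise. This assumes three sessions a week and a progression rule counted from week 1.

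It would be wrong to conclude that the main comparison is compromised. The primary outcomes (lumbar spine BMD, SPPB and the SF-36 summary scores) use neither adherence nor dose.

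**What to change.** 1. Change item 2 of the Precautions row in Table 4.3.1 (1) to exhaling when exerting force and inhaling when relaxing, in line with the intensity row. Have the responsible clinicians confirm the direction, since the protocol does not say which version is right. Carry the same text into the training manual.
2. Change Section 1.4.1 to three sessions a week. State the number of training weeks and the resulting planned session count as the adherence denominator (96–105 if 32–35 weeks is adopted).
3. State one set schedule consistent with the maximum of three: either the third set starts at week 9, or two sets run through week 12 and the progression rule is reworded so that the third starts at week 13. Update the one-to-two-set wording in Tables 4.3.1 (1) and 4.3.1 (2) to match.

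The cost is protocol and manual wording, with no added procedures. Section 4.7.1 records ethical approval as pending, so on this document the changes can be made before approval.
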